Recent studies have highlighted the importance of exercise selection and angle specificity in resistance training, showing that different knee angles result in varied activation patterns in the quadriceps and hamstrings. However, current literature offers limited insight into the effects of integrating mini squat exercises with leg press training on injury prevention and functional outcomes in athletic populations. In particular, there is a lack of literature on how such a combined leg press and mini squat exercise at different angles influences the H:Q ratio, lower limb neuromuscular control, and performance in young male football players. Therefore, the present study aims to examine whether incorporating mini squats performed at varying knee flexion angles into a leg press training program can improve muscle balance and lower limb strength in football players. The findings may provide valuable guidance for physiotherapists, coaches, and sports scientists in developing evidence-based, angle-specific exercise protocols tailored to the functional demands of athletes. (**Watanabe et al., 2020**).

Delimitation:

This study will be delimited to the following:

1. Male football players aged between 18–30 years (**Scoz et al., 2021**).
2. Body Mass Index (BMI) between 18.5 and 24.9 kg/m² (**Walsh et al., 2018 & Sattar & Lean, 2009**).
3. Participants will receive 18 training sessions, conducted three days per week, over six successive weeks

Basic assumptions:

1. Participants understood and followed the given instructions during assessment and treatment procedures.
2. Participants did not receive any additional medical or physical therapy treatment during the study period.

Hypotheses will be:

1. There is no statistically significant difference between adding 30°, 45°, and 60° knee flexion mini-squat exercises to leg press exercise and leg press exercise alone on quadriceps strength in football players.
2. There is no statistically significant difference between adding 30°, 45°, and 60° knee flexion mini-squat exercises to leg press exercise and leg press exercise alone on hamstrings strength in football players.
3. There is no statistically significant difference between adding 30°, 45°, and 60° knee flexion mini-squat exercises to leg press exercise and leg press exercise alone on the hamstrings-to-quadriceps H:Q ratio in football players.

Definitions of terms

Hamstring-to-quadriceps ratio H:Q ratio:

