2. The participant's feet will be positioned shoulder-width apart on the footplate, with the toes slightly externally rotated and the heels in full contact with the platform.
3. The participant will maintain full contact with the backrest throughout the exercise, with the head and spine supported. The side handles will be grasped to enhance postural stability and balance.

4. The exercise will commence from a flexed knee position, with particular attention given to maintaining proper knee alignment over the feet, avoiding any medial or lateral deviation.
5. The participant will extend the knees and hips to press the platform upward, taking care to avoid full knee lockout at the end of the movement.
6. The platform will then be returned to the initial position in a controlled manner through knee flexion, maintaining proper form throughout the eccentric phase (figure 8).

[figure not shown]

Fig 8: Leg press exercise adopted from (adapted from Martín et al., 2020).

2) Experimental groups: The participant in each subgroup (A, B, and C) will perform the same leg press exercise protocol applied for group D followed by mini squat exercise program with 5 min of submaximal cycling on an ergometer between 2 treatment programs. A total of 18 sessions will be conducted over a six-week period as follows:

1. **Group A:** participants will receive mini-squat program at 30° in addition to leg press program
2. **Group B:** participants will receive mini squat program at 45° in addition to leg press program
3. **Group C:** participants will receive mini-squat at 60° in addition in addition to leg press program

Mini-squat program:

1. Participants will stand barefoot or wear flat training shoes on a stable surface, placing their feet shoulder-width apart with toes slightly pointed outward.
2. A goniometer will be used during the first session to measure the target knee flexion angle (30° for group A, 45° for group B, and 60° for group C) demonstrated once by the examiner on one leg while the participant stands still. This will be followed by passive guidance into the used angles to help the participant recognize the posture and depth, with instructions to remember the sensation for future sessions; goniometer use will be repeated in later sessions only if corrective feedback is required.

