3. Mini-squat session will last 10 minutes. Squat will be performed in a slow and controlled manner (approximately 2 seconds down and 2 seconds up), with short rests of 15–30 seconds allowed every 1–2 minutes as needed. Approximately six minutes of active squatting will be completed per session, with the remaining time allocated for brief rests and transitions (**adapted from Hartmann et al., 2016**) (figure 9).

Fig 9: Mini squat exercise (adopted from Prentice, 2024).

Statistical analysis

All analyses were carried out using IBM SPSS Statistics version 27 (IBM Corp., Chicago, IL, USA).

- Subject characteristics will be analyzed using ANOVA, while the Chi-squared test will be used to compare the distribution of the affected side among the groups
- The Shapiro-Wilk test assessed the normality of the data, followed by Levene's test to verify the homogeneity of variances across groups.
- A mixed MANOVA will be conducted to evaluate the effects of group on the dependent variable(s).
- Post-hoc multiple comparisons were performed with Bonferroni correction to adjust for Type I error.
- Statistical significance was determined at a threshold of $p < 0.05$.

REFERENCES

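### Knee angle is the only planned difference between groups A, B and C, yet its measurement is scheduled in the first of 18 sessions only, with no stated trigger for re-checking and no stated record of the achieved angle

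*Combined protocol and SAP*

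**What the plan says.** Step 2 of the Mini-squat program (Chapter III, Treatment procedures) sets out how the angle is established and kept. "A goniometer will be used during the first session to measure the target knee flexion angle", and that angle is "demonstrated once by the examiner on one leg while the participant stands still". The player is next guided passively into position, "with instructions to remember the sensation for future sessions". For the rest of the programme the rule is that "goniometer use will be repeated in later sessions only if corrective feedback is required".

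The other components are common to the three arms. Each experimental group "will perform the same leg press exercise protocol applied for group D followed by mini squat exercise program". Step 3 of the Mini-squat program gives one session length, one tempo and one rest pattern for all: "Approximately six minutes of active squatting will be completed per session". The Delimitation section fixes the course: "Participants will receive 18 training sessions, conducted three days per week, over six successive weeks".

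The Purposes of the study ask about differences between the three angles for quadriceps strength, hamstring strength and H:Q ratio. The Hypotheses are framed against leg press alone. The Statistical analysis section contains no measure of adherence or of achieved angle. A digital goniometer is listed under Instrumentation.

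**The concern.** Angle is the experimental variable for every comparison among A, B and C, and adjacent arms are only 15 degrees apart. After the first session the plan relies on the player's memory of a position and on re-checks made for correction. It does not say who decides that correction is needed, how a deviation would be noticed, how large it must be, or whether the angle found is written down.

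If players in A squat somewhat deeper than assigned and players in C somewhat shallower, the arms move closer together and the between-angle differences shrink. Without recorded angles, a finding of no difference has two readings that the data cannot separate: angle does not matter, or the angles were not kept apart. A positive finding could not be tied firmly to the nominal angles either. Neither problem can be repaired after the trial.

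**Working it through.** **Session count (from the plan).** 3 sessions per week × 6 weeks = 18, which agrees with the stated total. 18 − 1 = 17 sessions (94%) have no scheduled angle measurement. At about 6 active minutes and 4 seconds per squat (2 down, 2 up), a session holds 6 × 60 / 4 = 90 squats. That makes 17 × 90 = 1,530 of 18 × 90 = 1,620 squats.

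**Inputs for an illustration.** From the plan: targets of 30, 45 and 60 degrees; 15 players per arm, 60 in total; alpha 0.05; Bonferroni-adjusted pairwise comparisons. Assumed, because the documents do not give them:
- response linear in angle;
- convergence of δ = 2.5, 5 or 7.5 degrees towards 45 in both A and C;
- a standardised A–C difference d of 0.8, 1.2 or 1.5 when the angles are delivered as planned;
- all six pairs among four groups tested, so alpha = 0.05/6 = 0.0083.

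**Contrast that remains.** The A–C separation is (60 − δ) − (30 + δ) = 30 − 2δ degrees, so the share kept is r = (30 − 2δ)/30:
- δ = 2.5: 25/30 = 83%
- δ = 5: 20/30 = 67%
- δ = 7.5: 15/30 = 50%

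**Power for A against C.** Two-sided noncentral t with 60 − 4 = 56 degrees of freedom and noncentrality d × r × √(15/2). For d = 1.2 this is 1.2 × 2.739 = 3.29 with no convergence, and 3.29 × 0.667 = 2.19 at δ = 5.

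| d | no convergence | δ = 2.5 | δ = 5 | δ = 7.5 |
|---|---|---|---|---|
| 0.8 | 30% | 19% | 11% | 6% |
| 1.2 | 71% | 51% | 30% | 15% |
| 1.5 | 91% | 75% | 51% | 26% |

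The pattern does not depend on dividing by six. At d = 1.2 the same row is 79%, 61%, 40% and 21% for alpha 0.05/3, and 90%, 77%, 58% and 37% for an unadjusted 0.05.

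**Random error centred on the target.** This does not shrink the mean contrast; it only adds outcome variance. With d = 1.2 over 30 degrees the slope is 0.04 SD per degree. A between-player angle SD of 5 degrees inflates the outcome SD by √(1 + (0.04 × 5)²) = 1.020, and an SD of 10 degrees by √(1 + (0.04 × 10)²) = 1.077. The effective d becomes 1.18 or 1.11, and power falls from 71% to about 69% or 62%. Systematic convergence is therefore the main threat to power; scatter matters much less.

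**The case against.** The plan does not leave the angle to memory alone. Step 2 includes passive guidance into the position, and it permits the goniometer again whenever correction is needed. That is fair and narrows the gap, but does not close it: the permission carries no trigger, tolerance, schedule or record, so a deviation nobody notices prompts no measurement.

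The documents give no drift, no direction of drift and no SD of achieved angle. If all three arms moved the same way by the same amount, their separation would be intact; only convergence biases the comparisons towards no difference. That stands, and it is why the figures above are illustrations.

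A reader might infer that the arms could become indistinguishable. The documents do not support that, and even the largest convergence assumed here leaves half of the A–C contrast. Nor do they say that correction is judged by eye, or that angles will not be recorded; they are silent on both.

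A reader might also blame low power for the between-angle comparisons on the goniometer rule. Under the same linear model with d = 1.2 for A–C, adjacent arms differ by d = 0.6, and power at 0.05/6 is about 15% with perfect delivery. That is mainly a matter of sample size.

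Finally, the formal hypotheses compare each angle programme with leg press alone. Group D has no mini-squat programme, so those comparisons largely survive.

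**Conclusion.** The point holds for the comparisons among A, B and C. The one variable that separates them has no scheduled measurement in 17 of 18 sessions and no stated record. That a null between-angle result would be uninterpretable follows from the text alone and needs no drift figure.

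The loss of power is conditional on convergence, a linear response, the assumed d and the assumed number of comparisons. For 5 degrees of convergence in both A and C it runs from 30% to 11% at d = 0.8, and from 91% to 51% at d = 1.5. This is a cheap improvement to delivery and reporting; it does not show that the angles will drift.

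**What to change.** In step 2 of the Mini-squat program, replace the rule that limits later goniometer use to corrective feedback with a scheduled check of the bottom-position angle in groups A, B and C. It should be at least weekly and ideally at every session. Correct the player to the assigned angle, record the angle achieved before correction, and state the tolerance that prompts correction. Add to the Statistical analysis section that achieved angle will be summarised by arm (mean and SD) alongside the results. A physical depth marker is optional, since it adds a cue to a programme built on remembered position. No target angle changes.

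The cost is one line on the session record and an estimated minute per check, with the goniometer already listed. For 45 players, weekly checks come to 45 × 6 = 270 measurements, and checks at every session to 45 × 18 = 810.

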Isokinetic dynamometry, most commonly performed using systems such as the Biodex, is considered the gold standard for assessing quadriceps and hamstring performance. It provides dynamic, objective, and reproducible measures of torque during concentric and eccentric contractions under controlled angular velocities (**Drouin et al., 2004**). In addition to peak torque, this method yields further performance parameters including total work, power, and fatigue index that offer a comprehensive understanding of muscular capacity (**Impellizzeri & Marcora, 2009**).

A distinct advantage of isokinetic dynamometry lies in its ability to assess the H:Q ratio. The conventional H:Q ratio is defined as the relationship between concentric hamstring and concentric quadriceps peak torque, whereas the functional H:Q ratio compares eccentric hamstring to concentric quadriceps torque (**Aagaard et al., 1998**). These indices are valuable for evaluating muscular balance across the knee joint, informing injury risk assessment,

rehabilitation progress, and return-to-sport readiness (Coombs & Garbutt, 2002).

The validity of isokinetic dynamometry is well established. Torque is measured directly via the device's lever arm at predefined angular velocities, demonstrating strong criterion validity in comparison with other strength assessment methods. Furthermore, the ability to isolate joint movements and regulate contraction speed enhances construct validity, making it particularly suitable for both clinical practice and research applications (Feiring et al., 1990).

Reliability has been consistently confirmed across studies. Test-retest reliability of isokinetic quadriceps and hamstring strength has shown excellent results, with ICCs ranging from 0.85 to 0.99 depending on contraction mode and angular velocity (Maffiuletti et al., 2007; Impellizzeri & Marcora, 2009). H:Q ratio measurements similarly demonstrate strong reproducibility, with ICCs typically reported between 0.82 and 0.95 (Ayala et al., 2012). The standard error of measurement (SEM) for peak torque generally falls between 5–8%, indicating minimal variability due to measurement error (Dirnberger et al., 2012). Moreover, Biodek dynamometers have demonstrated high inter-device reliability, ensuring consistent outcomes across different testing sites (Feiring et al., 1990).

- **Assessment of range of motion ROM:**

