SUBJECTS, MATERIALS AND METHODS

The current study aims to investigate whether incorporating mini squat exercises at different knee flexion angles into a leg press training program enhances hamstring- quadriceps ratio H:Q ratio in football players.

Design of the study:

This study will follow a randomized controlled trial (RCT) design.

Study setting

The study will be conducted at the outpatient physical therapy clinic of Jazan University Hospital, kingdom of Saudi Arbia.

Sample size:

The sample size for this study was determined using G*Power version 3.1.9 (Heinrich-Heine-University, Düsseldorf, Germany). An a priori power analysis was conducted for a repeated measures MANOVA with between-subject factors, setting the alpha level (α) at 0.05, desired power ($1 - \beta$) at 0.80, Pillai's trace (V) at 0.1989, and effect size $f^2(V)$ at 0.2877, targeting isometric muscle strength across four independent groups. The analysis indicated a minimum required sample size of 48 participants, allocating 12 per group. To compensate for possible dropouts, the total sample was increased to 60 participants, with 15 individuals per group (**Wirth et al., 2016**) (figure 3).

[figure not shown]

Fig 3:sample size calculation using G power

Randomization, allocation concealment, and blinding

The enrolled participants will be randomized in a simple randomization way using (www.randomizer.org/links/) by another participant not involved in the data collection. Allocation concealment will be ascertained using sealed, opaque, sequentially numbered envelopes. The participants will be blinded to the assigned intervention group.

Participants

Sixty male football players from Al-Ahli and Al-Ittihad football clubs in the Kingdom of Saudi Arabia. Participants will be asked to sign a written informed consent that includes participation in the experimental trial, permission to use data and/or pictures, and informing them of their right to withdraw at any time (**Appendix I**).

Participants will be randomized into 4 equal groups: an experimental group (A, B, and C), and a Control group (D).

Experimental groups (A, B, and C)

Group A: Fifteen participants will receive mini-squat exercises at 30° knee flexion and leg press exercises

Group B: Fifteen participants will receive mini-squat exercises at 45° knee flexion and leg press exercises

Group C: Fifteen participants will receive mini-squat exercises at 60° and leg press exercises

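### The plan does not say which term of the pre/post mixed MANOVA decides each hypothesis; read literally it names the between-subject group effect, the weaker test of a training effect

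*Combined protocol and SAP*

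**What the plan says.** Under Assessment procedures, the same tests are done at a pre-test and again three days after the last session, so each outcome has two analysed values per player. The Hypotheses section has three statements, one each for quadriceps strength, hamstring strength and the H:Q ratio. Each sets the mini-squat arms against leg press alone; the first ends "to leg press exercise and leg press exercise alone on quadriceps strength in football players". The Significance section gives the aim as whether the added exercise "can improve muscle balance and lower limb strength in football players".

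The Statistical analysis section has one sentence on the main test, "A mixed MANOVA will be conducted to evaluate the effects of group on the dependent variable(s"), and one on follow-up, "Post-hoc multiple comparisons were performed with Bonferroni correction to adjust for Type I error". The Sample size section describes a "repeated measures MANOVA with between-subject factors", with Pillai's V of 0.1989 and an effect size "at 0.2877, targeting isometric muscle strength across four independent groups". It concludes: "The analysis indicated a minimum required sample size of 48 participants, allocating 12 per group". Enrolment is then raised to 60.

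No readable text names time, group x time, change from baseline or baseline adjustment.

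**The concern.** A mixed model with four groups and two time points yields a group effect averaged over time, a time effect and a group x time interaction. Only the interaction, or a post-test comparison adjusted for the pre-test, isolates what training did. The group effect averages the pre-test, where randomised arms are equal in expectation, with the post-test. It therefore halves a real post-test difference and keeps most of the variation between players.

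Two things are at stake. A reader cannot tell in advance which result decides each hypothesis, so the choice could be made after the results are seen. And if the term literally named were the one to decide, the trial could miss an effect that its own data would detect with a better-chosen term.

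**Working it through.** **Inputs.** From the Sample size section: V = 0.1989, 0.2877 given as f²(V), α = 0.05, four groups, N = 48 raised to 60. Assumed: the pre-post correlation ρ, which the documents do not give, taken as 0.3 to 0.95; equal variance at both tests; equal expected pre-test means (randomisation). The nearest documented figure is test-retest reliability of isokinetic strength, "with ICCs ranging from 0.85 to 0.99 depending on contraction mode and angular velocity", which may exceed the correlation across six weeks of training.

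**Reproducing N = 48.** For one response, f² = V/(1−V) = 0.1989/0.8011 = 0.2483, so f = 0.498. With noncentrality λ = f²N = 0.2483 × 48 = 11.9 on 3 and 44 degrees of freedom, power is 80.0%. At N = 60 it is 89.3%. Taking 0.2877 as f² gives 86.0% at N = 48, so f = 0.498 is used below.

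**Effect size by term.** Let f be the post-test between-group effect in units of the within-group SD, σ.
- Group effect (mean of pre and post): signal halved, variance σ²(1+ρ)/2, so f² becomes f²/[2(1+ρ)].
- Group x time (post minus pre): full signal, variance 2σ²(1−ρ), so f²/[2(1−ρ)].
- ANCOVA: full signal, residual variance σ²(1−ρ²), so f²/(1−ρ²), with one error degree of freedom fewer.

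The ratio of the first noncentrality to the second is (1−ρ)/(1+ρ): 1/3 at ρ = 0.5 and 1/9 at ρ = 0.8. For example, at ρ = 0.5 the three values of f² are 0.2483/3 = 0.083, 0.2483/1 = 0.248 and 0.2483/0.75 = 0.331.

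**Case A: f = 0.498 is the post-test effect.** Power at α = 0.05 from the noncentral F:

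| ρ | Group, N = 48 | Group, N = 60 | Group x time, N = 48 | ANCOVA, N = 48 |
|---|---|---|---|---|
| 0.3 | 38% | 47% | 64% | 84% |
| 0.5 | 33% | 41% | 80% | 91% |
| 0.8 | 28% | 35% | >99% | >99% |
| 0.95 | 26% | 32% | >99% | >99% |

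**Case B: f = 0.498 is the group x time effect.** That term has 80% power at N = 48 and 89% at N = 60. The group effect then has f² = 0.2483 × (1−ρ)/(1+ρ). As ρ rises from 0.3 to 0.95, its power falls from 51% to 7% at N = 48 and from 62% to 7% at N = 60.

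**Case C: f = 0.498 is the group effect itself.** That term has 80% at N = 48 by construction. The post-test effect must then be √[2(1+ρ)] times 0.498: a factor of √2.6 = 1.61 at ρ = 0.3 and √3.9 = 1.97 at ρ = 0.95.

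**Checks.** Simulation of the single-outcome tests (4,000 trials per cell, 12 and 15 per arm, ρ of 0.5 and 0.8) gave null rejection rates of 4.8–5.5% across the three tests and power within 2 points of the formulas. A two-outcome MANOVA was also simulated (15 per arm, assumed correlation 0.6 between outcomes, post-test f = 0.498 on each). At ρ = 0.5, 0.8 and 0.9 it gave 36%, 31% and 29% for the group effect, against 88%, 100% and 100% for group x time.

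**The case against.** The strongest reply is that the wording is loose rather than wrong. The sentence speaks of effects in the plural within a mixed model, never says main effect or averaged over time, and may simply echo hypotheses that are themselves between-group statements. Group x time is also an effect involving group. That stands, so a reader who infers that the team has chosen a low-power test goes further than the documents do: they show an unspecified term. Nor do they show that the trial is underpowered. In Case B, with the interaction deciding, the plan meets its own 80% target.

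The reply does not close the gap. The Sample size section also speaks only of between-subject factors. Its figures fit a between-group test over three uncorrelated measurements as well (3 × 0.2877² = 0.2483, the same f² as above), so the between-group wording cannot be dismissed as a slip. This does not prove which procedure was run, since a single response with f = 0.498 also gives 80.0%. The sample size figure (Fig 3) is not reproduced in the text available and might settle it.

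Two limits also stand. The percentages come from a single-outcome approximation, not the planned MANOVA; the two-outcome simulation supports the ranking, not the exact values. And a reader might derive much lower power by using 0.2877 as f with λ = f²N. That reading gives only 33% at N = 48 even for a plain four-group comparison, so it does not match the plan's own calculation and is not relied on here.

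**Conclusion.** The point holds as a gap in specification with a better analysis available from the same data. No readable text ties a term to any of the three hypotheses or to the Bonferroni comparisons. The term literally named is weaker than group x time at every positive pre-post correlation, given equal expected pre-test means.

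The low power is conditional on the group effect deciding and on the planning effect belonging to another quantity: 26–47% across both sample sizes if f = 0.498 is a post-test effect, and 7–62% if it is a group x time effect. If it belongs to the group effect itself, the 80% stands, but only for a post-test effect 1.61 to 1.97 times larger. The sizes depend on the assumed ρ; the ranking of the group effect below group x time does not. There is no inflation of Type I error from using any one of these terms.

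**What to change.** Replace the main-analysis sentence with, for example: For each outcome in the hypotheses (quadriceps strength, hamstring strength, H:Q ratio), post-test values will be compared between the four groups by ANCOVA with the pre-test value of that outcome as covariate, followed by Bonferroni-adjusted comparisons of adjusted means. MANCOVA would keep a single multivariate test. Alternatively, keep the mixed MANOVA, name group x time as the deciding term for each hypothesis, and tie the Bonferroni comparisons to it. If ρ is as high as 0.85 the choice between the two matters little, since the variance ratio is 2/(1+ρ) = 1.08.

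With either option, restate the sample size basis for the chosen test, saying which effect the planning figure describes and what ρ is assumed. If the outcomes are tested separately, state how they share the 5%: three independent unadjusted tests would give 1 − 0.95³ = 14.3%. Settle this before any group comparison is seen.

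No new data, visits or software are needed. ANCOVA costs one degree of freedom per covariate. A 0.05/3 rule lowers ANCOVA power from 91% to 80% at f = 0.498, N = 48 and ρ = 0.5.

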- The isokinetic device will record key outcome measures including peak torque (Nm), average power, and total work for each repetition. These values will be used to quantify quadriceps strength (figure 7).

2- Measurement of hamstrings muscle strength:

All previously described quadriceps muscle evaluation procedures will be applied for the hamstrings muscle strength test; however, the range of motion will be set from full knee extension, and the participant will be instructed to actively bend the knee against the resistance of the device to 90°.

3-Hamstring to quadriceps H:Q ratio calculation:

H:Q ratio will be calculated by use this formula:

$$H:Q \text{ Ratio} = \left(\frac{\text{Hamstring Peak Torque (Nm)}}{\text{Quadriceps Peak Torque (Nm)}} \right)$$

- Value interpretation:

- < 0.5: hamstring weakness.
- 0.5-0.7: normal range.
- 0.8-1: strong hamstring.

Fig 7: quadriceps and hamstring muscles strength measurement by isokinetic dynamometer device (adopted from Sinacore et al. 2017).

Treatment procedures:

1) Control group D: The participant will receive 18 sessions of leg press exercise using a leg press machine, conducted over a six-week period. Each training session will consist of 7 sets of 10 repetitions, with inter-set rest intervals of 90 seconds (**Wirth et al., 2016 a)** Before starting the leg press program, a standardized warm-up consisted of 5 min of submaximal cycling on an ergometer and 2 to 3 sets of moderate loaded squats with 6 repetitions each.

10 Repetition Max (10RM) Test:

The 10-repetition maximum (10RM) test will be conducted to determine the initial training load as a following:

- The machine will be loaded with a light weight (approximately 25–30% of the participant's body weight).
- The participant will perform 10 repetitions using proper form.
- The weight will be increased gradually (by 5–10 kg) after each successful attempt.
- This process will continue until the participant reaches a weight they can complete for 10 repetitions with good form, but with difficulty during the final 2 reps.
- That weight will be recorded as the participant's 10 Repetition Maximum (10RM).
- Strength training will then begin at 75–85% of the determined 10RM (**Piper et al., 2021**).

Leg Press Exercise:

1. The seat and backrest of the leg press machine will be adjusted to position the participant's hips and knees at approximately 90 degrees of flexion to ensure a comfortable and standardized starting posture.

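### The only named group test is one mixed MANOVA on unlisted outcomes: it cannot settle the H:Q hypothesis, and it loses power if H:Q enters alongside its own two components

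*Combined protocol and SAP*

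**What the plan says.** - **Hypotheses (Chapter I).** There are three separate null hypotheses, for quadriceps strength, hamstring strength and the ratio. The third compares the mini-squat programs with leg press "alone on the hamstrings-to-quadriceps H:Q ratio in football players". The aim at the start of Chapter III names only the H:Q ratio.
- **Assessment procedures (Chapter III).** "H:Q ratio will be calculated by use this formula": hamstring peak torque divided by quadriceps peak torque. All tests are done before training and again after it, so there are two time points.
- **Statistical analysis (Chapter III).** The group-effect test is given in one sentence: "A mixed MANOVA will be conducted to evaluate the effects of group on the dependent variable(s"). Bonferroni-corrected post-hoc comparisons follow. Neither sentence says which outcomes are meant, and the size of the Bonferroni family is not given.
- **Sample size (Chapter III).** "An a priori power analysis was conducted for a repeated measures MANOVA with between-subject factors", with alpha 0.05, power 0.80, V = 0.1989 and an effect size of 0.2877. "The analysis indicated a minimum required sample size of 48 participants, allocating 12 per group". This was raised to 60 for dropout.

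**The concern.** Three hypotheses and one test suggest a three-variable MANOVA. If peak torque is the strength measure, H:Q is an exact function of the other two variables. (The device also records average power and total work.) A ratio placed beside its numerator and denominator uses degrees of freedom and tells the test little that is new.

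The larger problem is interpretation. A joint test asks whether the groups differ on some combination of the outcomes. The third hypothesis asks whether they differ on one of them, and that one is the outcome named in the Chapter III aim. A significant joint result could be reported as a change in muscle balance when both muscles had simply become stronger together.

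**Working it through.** **1. The plan's own sample size.** Inputs from the Sample size section: effect 0.2877, four groups, alpha 0.05, N = 48. The text does not give the number of measurements m or their correlation ρ. For a repeated measures MANOVA, between factors, λ = N·f²·m / (1 + (m − 1)ρ), referred to F(3, N − 4). With 0.2877 taken as f, m = 3 and ρ = 0 (all inferred):

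- λ = 48 × 0.2877² × 3 = 11.92
- V = λ / (N + λ) = 11.92 / 59.92 = 0.1989
- power = 0.800

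Both stated figures reproduce. Only two time points are planned, so m = 3 fits three outcomes better than three visits. That supports the three-variable reading but does not prove it. The 80% belongs to a test with 3 numerator df, not to a two- or three-variable Pillai test.

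**2. Cost of a redundant third variable.** With two time points, the group-by-time test in a mixed MANOVA is a MANOVA on change scores. For p variables and four groups: s = min(p, 3), f² = V / (s − V), λ = N·s·f², df1 = 3p, df2 = s(N − 4 − p + s). V is held at 0.1989, meaning that the third variable brings no group information of its own.

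- p = 2: f² = 0.1989 / 1.8011 = 0.1104
- p = 3: f² = 0.1989 / 2.8011 = 0.0710

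| N | p | λ | df | Power |
|---|---|---|---|---|
| 48 | 2 | 10.60 | 6, 88 | 63.8% |
| 48 | 3 | 10.23 | 9, 132 | 54.3% |
| 60 | 2 | 13.25 | 6, 112 | 76.0% |
| 60 | 3 | 12.78 | 9, 168 | 66.9% |

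The losses are 63.8 − 54.3 = 9.5 points and 76.0 − 66.9 = 9.1 points. The N for 80% power, in multiples of four, is 68 with two variables and 80 with three. Holding λ fixed at 11.92 instead of V gives a loss of 7.4 points at N = 48.

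**3. How far the loss moves.** Simulated Pillai tests (20,000 runs each, 15 per group, fully redundant third variable, group differences along one dimension) gave:

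| Two variables | Three variables | Loss (points) |
|---|---|---|
| 67.5% | 56.4% | 11.1 |
| 82.6% | 72.7% | 9.9 |
| 92.3% | 85.5% | 6.8 |
| 97.4% | 93.9% | 3.5 |

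Simulations with the actual ratio, using assumed coefficients of variation, correlations and effects, gave losses from about 0 to about 12 points. Near the bottom of that range, power fell from 99.5% to 98.9%.

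**4. How redundant H:Q is.** The documents give no standard deviations or correlations. Assuming coefficients of variation of 10–20%, a quadriceps–hamstring correlation of 0.5–0.7 and a pre–post correlation of 0.8–0.9, R² of H:Q on its two components is 0.94–0.99 for post values. For change scores it is mostly 0.81–0.96, with one value of 0.49 at a coefficient of variation of 20%.

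**5. Whether the joint test can answer the H:Q question.** If both torques rise by the same proportion g, then H(1 + g) / Q(1 + g) = H/Q, so the ratio does not move. In simulation with equal standardised gains in the two muscles, 15 per group and the largest gain tried, the three-variable test rejected in 67% of trials. A test of H:Q alone rejected in about 5%, its nominal level.

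**The case against.** The plan never says that H:Q enters the MANOVA with its components. A reader might infer that it does, but that is an inference from three hypotheses, one test and a sample size that fits three measurements. It must stay conditional.

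A reader might also infer that the trial falls about 9 to 10 points short of its planned 80%. The documents do not support that. The figure holds for full redundancy at fixed V and middling power, and the 80% was computed for a different test. Outside those conditions the loss can be negligible.

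Nor is near-singularity of the covariance matrix a further harm. H/Q is a nonlinear function of H and Q, so the matrix has full rank and Pillai's trace remains valid. The cost is the extra degrees of freedom, already counted in the power loss.

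Finally, post-hoc comparisons are planned. They are usually made outcome by outcome and could address H:Q. This stands in part: the plan does not say which outcomes they cover, how many comparisons the correction spans, or whether they depend on a significant joint test. They are not yet a prespecified test of the third hypothesis.

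**Conclusion.** The point holds in conditional form, and the plan should be changed. On the natural reading, the one named test contains a ratio and both its components. A fully redundant third variable then costs 9.5 points of power at N = 48 and 9.1 at N = 60, at V = 0.1989. Across the assumed inputs the loss is roughly 0 to 12 points, largest when two-variable power is about 60–85%.

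The interpretive defect does not depend on those assumptions: a significant joint test cannot establish that H:Q differs between groups. The other reading does not rescue the plan, because leaving H:Q out removes the only named group-effect test for the third hypothesis.

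**What to change.** In the Statistical analysis section:

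1. List the dependent variables, and state that strength means peak torque if that is intended.
2. Keep H:Q out of any MANOVA that contains hamstring and quadriceps torque. If a MANOVA is kept, restrict it to the two torques.
3. Test each of the three hypotheses in its own model of the post-training value on group, adjusted for that outcome's baseline. Analysing log H:Q is optional.
4. State the multiplicity control across the three outcomes and across the pairwise group comparisons.

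This changes analysis wording only. The data are already to be collected, and the models are available in the stated software. The downside is that one omnibus test becomes three outcome-specific tests that need a stated adjustment. The power calculation should be redone for the tests actually used.
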